4.3 Randomized Groups

Control Group 1: Atraumatic extractions followed by grafting with Bone Allograft mixed with sterile saline and collagen plug.

Test Group 2: Atraumatic extractions followed by grafting with Bone Allograft mixed with Amnion graft and collagen plug.

4.4 Pre-surgical Procedures

Conventional oral impressions will be made and a temporary Essix retainer will be fabricated. The Essix retainer, a removable prosthesis, will protect the healing tissue in an aesthetically pleasing manner but will not impede the clinical observation of study sites. Study casts may also be used to fabricate a surgical guide prior to implant surgery.

4.5 Surgical Extractions

All surgeries will be performed by qualified clinicians/investigators in an appropriately equipped surgical operatory located in the Periodontal Clinic at UAB School of Dentistry.

Prior to extraction surgery, participants will be given a loading dose of antibiotics based on their medical history and concomitant medications. A suggested prophylactic regimen follows:

2 gm of Amoxicillin 1 hour prior to the procedure followed by 500 mg (TID) for 7 days
Patients with reported allergy to Amoxicillin:
600mg Clindamycin 1 hour prior to the procedure followed by 300 mg (TID) for 7 days

The facial area will be scrubbed with 2% Clorhexidine soap and the oral cavity disinfected by rinsing for 1 minute with a 0.12% chlorhexidine gluconate antimicrobial oral rinse. Prior to extractions clinical photographs will be taken from the buccal and occlusal aspects. Photographs will be taken in a 1:1 ratio using a Nikon D-7000.

After preparation and isolation of the surgical area, anesthesia will be achieved in the region by regional block or local infiltration. Conscious sedation may be added at the surgeon's discretion to help manage patient anxiety.

The teeth will be extracted as atraumatically as possible, without raising a flap, utilizing periotomes, luxators and the Easy Extrac system. In both groups, the integrity of the remaining socket walls will be assessed and measurements recorded on the surgical CRF. The sockets will be debrided and a bleeding surface created by decorticate the socket walls with either a curette or a surgical round burr.

4.6 Grafting Extraction Sockets

After extractions, sockets will be grafted according to each participant's assigned randomization group.

Group-1: Each socket will be grafted with Bone Allograft mixed with sterile saline.

4.6.1a Irrigate sockets with sterile saline.

4.6.1b Pack the graft into each of the study sites using mild pressure achieving complete fill of the sockets.

4.6.1c Trim a 3 mm section of collagen plug and secure it over the grafted areas with 5.0 Monocryl crossing mattress sutures.

Group-2: Each socket will be grafted with Amnion Graft mixed with Bone Allograft

4.6.2a Irrigate sockets with sterile saline.

4.6.2b Pack the graft into each of the study sites using mild pressure achieving complete fill of the sockets.

4.6.2c Trim a 3 mm section of collagen plug and secure it over the grafted areas with 5.0 or 6.0 Monocryl crossing mattress sutures.

After completion of procedures, the Essix retainer will be fitted and placed.

A baseline, post-grafting CBCT scan will be made to include images of each study site. Prescriptions for anti-bacterial mouth wash, antibiotics, and pain relief will be provided based on individual patient

needs. An ice-pack will be dispensed. Verbal and written home care instructions will be given and the patient will be scheduled for a follow-up appointment.

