Procedures	
Only treatment of non-adjacent sites will be included in the database. Each participant may have up to four non-adjacent sites selected for inclusion as study treatment sites.
 
Extractions Atraumatic extractions and graft procedures following the randomization table and standardized surgical procedures.
 
Three-dimensional images, acquired through Cone Beam Computed Technology (CBCT), will be captured immediately post-grafting. Prophylactic antibiotics will be dispensed, prescriptions for post-surgery antibiotics and analgesics (prn) will be written. Antibacterial mouth wash will be dispensed; written and verbal patient home-care instructions will be provided.
 
To preserve anterior aesthetics, during the healing phase, an Essix retainer will be made for each participant and inserted immediately after the extractions/grafting procedures.
 
Follow-up evaluations Performed at week-1, week-2, week-4, and week 7 will include:
 
 Assessment of post-surgical healing Assessment of adverse experiences Measurement of clinical parameters Clinical photographs Suture removal at week 2 A CBCT scan will be completed at week-7 
Biopsy and Implant Placement A biopsy, and surgical placement of implants completed at week-8
 
 Prophylactic antibiotics dispensed Pre-surgical oral rinse One bone-fill biopsy per patient, harvested by trephine (placed in fixative for later histological analysis) Measurement of clinical parameters Clinical photographs Surgeon's subjective observation of osseous fill quality (D-1-D-4). Measurements of torque at implantation will be recorded Immediate post-surgical intra-oral radiographs Prescriptions for post-surgery antibiotics and analgesics (prn) Antibacterial mouth wash and ice-packs dispensed Written and verbal home-care instructions 
Post-Insertion Follow-up Implant surgical follow-up assessment and suture removal will be performed after two-weeks.

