2.3 Hypotheses and Specific Aims

The trial will test two hypotheses:

Hypothesis-1: Grafting with Bone Allograft is an efficacious method of enhancing the development of new bone fill in extraction sockets.

Hypothesis-2: Bone Allograft/Amniotic allograft will aid osseous healing and will preserve alveolar ridge dimensions of extraction sockets more effectively than extraction sites grafted with Bone Allograft alone.

Specific Aims

- 1: Compare the efficacy of bone grafting with and without enrichment with amnion.
- 2: Compare alveolar ridge dimensions between groups after 7 weeks of post-extraction healing.
- 3: Compare soft tissue healing between groups at week-1, week-2, week-4 and after 7 weeks of post-extraction healing.

- 4: Assess quantitative bone fill between groups after 7 weeks of post-extraction healing
- 5: Compare qualitative bone fill between groups after 7 weeks of post-extraction healing.
- 6: Assess and compare the relationship of osseous healing and implant stability at insertion across groups after 8 weeks of post-extraction healing.
- 7: Compare implant stability between groups at 12 months and 24 months post-restoration.
- 8: Assess changes in longitudinal crestal bone level between groups at 12 and 24 months after permanent prosthetic attachment.

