4.7 Surgical Extraction Data Collection

The following data points will be collected and recorded on the surgical CRF: A description of the integrity of each of the socket walls will be recorded as follows.

4.7.1 Measurements of the Mesio-distal distance and the buco-lingual distance of the socket walls.

4.7.2 Measurements of dehiscence and fenestration defects made with a UNC-15 periodontal probe in relation to the adjacent socket crest and rounded up to the nearest millimeter.

4.7.3 Wound Measurements – Mesio-distal distance and bucco-lingual distance of the soft tissue wound margins after suturing made with a UNC-15 periodontal probe and rounded to the nearest millimeter.

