4.8 Post-Extraction Evaluations

Participants will return to clinic for oral evaluations as close to 7-days after the extraction/grafting procedure as possible and again at 14 days; sutures will be removed at the 14-day visit. Additional follow-up visits will be scheduled approximately 4 weeks and 7 weeks following grafting. Healing will be closely monitored and appropriate data recorded on follow-up CRFs.

At each visit, medical history will be reviewed and any changes documented. Information regarding adverse events will be captured and recorded following IRB and Federal reporting guidelines. At the 7-week post-grafting visit a second CBCT scan will be obtained.

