13.2 Subjective data

Observations of bone quality (D1-D-4) recorded by surgeons at implant placement.

Clinical observations of post-extraction soft-tissue healing

Clinical observations of soft-tissue and osseous response to dental implants

Clinical observations of overall aesthetic appearance

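### The test arm may be closed with 5.0 or 6.0 sutures and the control arm only with 5.0, with no rule for choosing in the supplied text, so closure can differ between arms as well as graft.

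*Combined protocol and SAP*

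**What the plan says.** Section 4.6 (Grafting Extraction Sockets) gives three steps per arm. In Group 1, the control, step 4.6.1c says to trim the collagen plug and "secure it over the grafted areas with 5.0 Monocryl crossing mattress sutures". In Group 2, the test arm, step 4.6.2c says to "secure it over the grafted areas with 5.0 or 6.0 Monocryl crossing mattress sutures".

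Elsewhere the protocol presents the graft mix as the contrast between arms. Section 4.3 (Randomized Groups) describes the test arm as "Atraumatic extractions followed by grafting with Bone Allograft mixed with Amnion graft and collagen plug". The control description is the same except that saline takes the place of amnion. The synopsis (Procedures) refers to "graft procedures following the randomization table and standardized surgical procedures".

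The outcome closest to wound closure is Aim 3 in section 2.3: "Compare soft tissue healing between groups at week-1, week-2, week-4", and again at week 7. Section 4.8 states that "sutures will be removed at the 14-day visit".

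**The concern.** A randomized comparison attributes a difference to the graft only if the rest of the procedure follows the same rule in both arms. Here the permitted closure depends on the arm. Randomization cannot balance that, because the assignment itself decides which sutures the surgeon may use. If 6.0 is used, suture size becomes a second treatment difference alongside amnion.

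At stake is the reading of early soft-tissue healing. Section 1.2 puts forward faster soft-tissue healing as a possible benefit of amniotic growth factors, so a difference at weeks 1 or 2 would naturally be credited to the product. Section 13.2 lists "Clinical observations of post-extraction soft-tissue healing" among the subjective data, and the only blinding stated in the supplied text is that of laboratory technicians (section 6.3).

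The two explanations could not be reliably separated afterwards. Suture size is not among the items listed for recording in section 4.7, and the analysis plan in 13.4 does not address it. The photographs in 9.4 document healing but do not show which factor caused it.

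**Working it through.** The plan states no figure on this point to reproduce. The check is a comparison of the text, followed by counts.

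**Step 1. The two procedures side by side (sections 4.6, 4.8)**

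| Element | Group 1 (control) | Group 2 (test) | Same? |
|---|---|---|---|
| Graft mix | bone allograft with saline | bone allograft with amnion | No, by design |
| Step a, irrigation | sterile saline | sterile saline | Yes |
| Step b, packing | mild pressure, complete fill | mild pressure, complete fill | Yes |
| Step c, plug | 3 mm piece of collagen plug | 3 mm piece of collagen plug | Yes |
| Step c, suture material and pattern | Monocryl, crossing mattress | Monocryl, crossing mattress | Yes |
| Step c, suture size | 5.0 | 5.0 or 6.0 | **No** |
| Suture removal | 14-day visit | 14-day visit | Yes |

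Apart from the graft mix, suture size is the only element that differs. No other section of the supplied text says when 6.0 should be chosen.

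**Step 2. Possible exposure**

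Inputs: 10 patients per group (section 3.1); one or more eligible teeth per patient (Table 1) and up to four study sites (section 4.1); all sites in a patient receive the same graft (section 4.2).

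- Fewest test-arm sockets: 10 × 1 = 10.
- Most test-arm sockets: 10 × 4 = 40.
- Let p be the share of test-arm sockets closed with 6.0. The documents do not state p, so it runs from 0 to 1, which means 0 to 40 sockets.
- Share permitted in the control arm: 0.
- Difference between arms: p − 0 = p, from 0% to 100%.

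This range shows what the text permits. It does not predict what surgeons will do.

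**Step 3. Outcomes within reach**

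- Aim 3 has four time points: weeks 1, 2, 4 and 7. Sutures are in place at week 1 and come out at the week 2 visit, so any direct effect falls mainly on 2 of 4.
- Section 4.7.3 records the "distance of the soft tissue wound margins after suturing made with a UNC-15 periodontal probe". That reading also comes after the step at which the arms can part.
- Of the eight specific aims, 1 is touched. The documents give no reason to expect an effect on histology, CBCT bone fill, insertion torque or implant survival, the last being the parameter labelled primary in 13.3.

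**The case against.** The strongest reply is that this is an editorial slip with no demonstrated consequence. Material, suture pattern, plug and removal day are the same in both arms. Group 2 may also use 5.0, so a surgeon can follow the protocol and close every patient identically. Nothing in the documents says that 6.0 rather than 5.0 changes healing, and a range of 0% to 100% says nothing about likely use. Allocation is by participant, so the number of sockets adds little to the argument. The wound measurement in 4.7.3 is taken on the day of surgery to the nearest millimetre, is not labelled an efficacy endpoint, and is unlikely to register a change of suture size. Section 4.3 does not mention sutures at all. A Manual of Procedures is listed as part of Appendix C and was not supplied; it may contain a closure rule.

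Much of this stands. The effect may be zero, the wording may be a slip, and the 4.7.3 point is secondary. That closure should match is an inference from how the arms are described; section 4.3 does not state it. The manual cannot be checked.

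None of this removes the discrepancy. An operative surgical step that differs by arm permits different practice until it is corrected, whether or not anyone intended it. If the manual does set one rule for both arms, section 4.6 should agree with it.

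**Conclusion.** The concern holds, as a minor point. The text difference is certain: the control arm has one permitted suture size, the test arm has two, and the supplied text has no rule for choosing. Closure is therefore a potential co-intervention tied to the assigned arm, and an actual one only if 6.0 is used.

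No size of bias is claimed, and it could be nil. The conclusion rests on two things the documents leave open: how often 6.0 would be used, and whether the unsupplied manual sets a common rule. It does not undermine the bone or implant outcomes. It is worth correcting because the documents give no reason for the asymmetry, so removing it gives up nothing they identify.

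**What to change.** Write the same suture specification into 4.6.1c and 4.6.2c: either one size for both arms, or both sizes with one rule for choosing that applies in both. Check that the Manual of Procedures agrees.

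Recording the size used on the surgical CRF is an optional check on adherence. It does not replace the text change. An analysis restricted to sockets closed with 5.0 would not be a remedy, because suture size is chosen after randomization and the restricted groups would no longer be the randomized ones.

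The cost is one line of protocol text and, if wanted, one CRF field. No extra staff, visits or patients are needed.

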4.7 Surgical Extraction Data Collection

The following data points will be collected and recorded on the surgical CRF: A description of the integrity of each of the socket walls will be recorded as follows.

4.7.1 Measurements of the Mesio-distal distance and the buco-lingual distance of the socket walls.

4.7.2 Measurements of dehiscence and fenestration defects made with a UNC-15 periodontal probe in relation to the adjacent socket crest and rounded up to the nearest millimeter.

4.7.3 Wound Measurements – Mesio-distal distance and bucco-lingual distance of the soft tissue wound margins after suturing made with a UNC-15 periodontal probe and rounded to the nearest millimeter.

4.8 Post-Extraction Evaluations

Participants will return to clinic for oral evaluations as close to 7-days after the extraction/grafting procedure as possible and again at 14 days; sutures will be removed at the 14-day visit. Additional follow-up visits will be scheduled approximately 4 weeks and 7 weeks following grafting. Healing will be closely monitored and appropriate data recorded on follow-up CRFs.

At each visit, medical history will be reviewed and any changes documented. Information regarding adverse events will be captured and recorded following IRB and Federal reporting guidelines. At the 7-week post-grafting visit a second CBCT scan will be obtained.

4.9 Tissue Biopsy and Implant Placement

After reviewing the CBCT scans the investigator will determine whether or not the sockets have enough bone-fill to enable the surgical placement of implants. The diameter and length of the implants placed will be determined by the surgeon/investigator based on the tooth location, anatomy, and bone volume determined from the CT scan prior to placement. Immediately prior to implant placement, a tissue biopsy will be harvested from the center of one grafted site. Implants will be placed following standard procedures outlined in the Manual of Procedures.

4.10 Implants Exposed

The implants will be exposed following the established recommendations and at the discretion of the implanting surgeon.

4.11 Implant Restoration

Each implant will be restored in the conventional manner with an aesthetically pleasing single crown restoration. When the permanent restorations are attached intra-oral radiographs and photographs will be obtained.

Table 2 – Study Procedures Visits -1 — 8

Procedures	V- (-1) Screening	V-1 Pre-Tx	V-2 EXT & Grafting	V-3 Week 1	V-4 Week 2	V-5 Week 4	V-6 Week 7 CBCT	V-7 Week 8 Implant placed	V-8 2 week Post-Op Evaluation
Consent Discussion/Obtained	X								
Medical History Review		X	X	X	X	X	X	X	X
Tx Plan Review		X							
Impressions		X							
Essix Retainer		X							
Randomized to Tx Groups		X							
Biopsy site selection		X							
Pre-Surg Antibiotics			X					X	
Pre-Surg Oral Rinse			X					X	
Tooth Extraction			X						
Tx Group Procedure			X						
Clinical Photographs			X	X	X	X	X	X	X
CBCT Scan			X					X	
Periapical Radiographs								X	
Post-Surg Instructions/Prescriptions				X					X
Suture Removal						X			X
AE's recorded			X	X	X	X	X	X	X
Bone Biopsy								X	
Implant Placement								X	
Torque Measurement									X

Table 3 Study Procedures Visits 9 —12

Procedures	V-9 Implant Exposed	V-10 Implant Restored	V-11 12 month	V-12 24 month
Medical History Review	X	X	X	X
Clinical Photographs	X	X	X	X
Periapical Radiographs		X	X	X
AE's recorded	X	X	X	X
Implants Exposed	X			
Sutures Removed (14 DAYS)	X			
Implant Restored		X		
Soft-tissue assessments			X	X
Pocket Depth Measurements			X	X

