4.2 Randomization

Participants will be stratified for smoking status and randomized to one of two extraction/grafting groups. In the case of multiple tooth sites within one participant, all the tooth sites will be assigned to receive the same graft material.

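### Table 2 allocates the arm one visit before extraction, and the reviewed text states no step that keeps it from the operator until grafting

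*Combined protocol and SAP*

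**What the plan says.** Table 2, which follows section 4.11, has a row "Randomized to Tx Groups" with its only mark at V-1 (pre-treatment). The row "Biopsy site selection" is marked at the same visit. Tooth extraction and the group-specific procedure are marked at the next visit, headed "V-2 EXT & Grafting".

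Section 4.2 gives the allocation method in one sentence: "Participants will be stratified for smoking status and randomized to one of two extraction/grafting groups". It adds that all sites in one participant receive the same material. It does not say who holds the sequence, how it is concealed or when the arm is disclosed. The synopsis (Procedures) refers to "graft procedures following the randomization table and standardized surgical procedures".

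Section 4.5 describes what happens at surgery before any graft is placed. The teeth are extracted, then "the integrity of the remaining socket walls will be assessed and measurements recorded on the surgical CRF", and the sockets are debrided and a bleeding surface is made by a step to "decorticate the socket walls with either a curette or a surgical round burr". Section 4.7 adds probe measurements of socket width and of dehiscence and fenestration defects.

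The arm is first used in section 4.6: "After extractions, sockets will be grafted according to each participant's assigned randomization group". The only blinding stated is that of the laboratory technicians who handle the biopsies (section 6.3).

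**The concern.** Between V-1 and the mixing of the graft the arm exists but nobody in the operatory needs it. Several operator-dependent steps fall in that interval: how gently the tooth is removed, how thoroughly the socket is debrided, which instrument is used to decorticate, and how wall defects are probed and recorded. If the operator knows the arm, these could differ between groups for reasons other than the graft.

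Socket handling could then affect the bone outcomes that the trial compares: ridge dimensions, bone fill and histology (section 2.3, aims 2, 4 and 5). Recorded defects could also make the groups look more or less alike at baseline than they are. In participants with more than one site, the single biopsy site could be chosen with the arm known.

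Allocating a visit early also leaves a gap in which a participant can be randomised and then not treated. Section 13.4 does not say how such a participant would be analysed.

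**Working it through.** **Order of events.** No formula applies here; the sections are set side by side.

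| Step | Where stated | When | Is the arm needed? |
|---|---|---|---|
| Randomisation | Table 2 | V-1 | – |
| Biopsy site selection | Table 2 | V-1, order relative to randomisation not stated | No |
| Extraction | 4.5, Table 2 | V-2 | No |
| Wall assessment and probe measurements | 4.5, 4.7.1, 4.7.2 | V-2 | No |
| Debridement and decortication | 4.5 | V-2, before grafting | No |
| Mixing and packing the graft | 4.3, 4.6 | V-2 | Yes |
| Soft tissue wound measurements | 4.7.3 | V-2, after suturing | Already known |

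**Could the table position be misread?** Some Table 2 marks sit one column later than the text: the second CBCT is under week 8 against week 7 in section 4.8, suture removal is under week 4 against day 14, and torque is under V-8 against implant placement in section 6.4. If the randomisation mark had moved in the same way, its true place would be screening, which is still before extraction. The order of the sections (4.2 before 4.5) and the wording of 4.6 agree with this.

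**Which routes reach a specified analysis?**
- Socket handling: it precedes every bone outcome, so an effect is possible.
- Probe measurements in 4.7.1 and 4.7.2: sections 13.1, 13.3 and 13.4 do not use them as an outcome baseline or covariate. The CBCT baseline is the scan taken just after grafting (sections 4.6 and 5.0). Radiographic bone height is compared with the value at insertion (section 13.3). The route therefore stops at the description of baseline comparability.
- Biopsy site: up to four sites per participant (4.1) and one biopsy each (6.3), so there is a choice wherever a participant has two or more sites.

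**Illustrative size.** The plan states no SD, effect size or power, so there is no figure of its own to reproduce. Inputs from the plan: 10 per group (3.1), two-tailed t test, α = 0.05 (13.4). Assumed: a systematic difference of d standard deviations in one continuous outcome with one value per participant, and no true graft effect.

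- Degrees of freedom = 10 + 10 − 2 = 18; critical value t = 2.101.
- Noncentrality = d × √(10/2) = 2.236 d.
- Rejection rate = P(|T| > 2.101), with T noncentral t on 18 df.

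| Assumed d (SD) | Noncentrality | Rejection rate |
|---|---|---|
| 0 | 0 | 5.0% |
| 0.1 | 0.224 | 5.5% |
| 0.2 | 0.447 | 7.1% |
| 0.3 | 0.671 | 9.7% |
| 0.5 | 1.118 | 18.5% |

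**Losses.** One participant lost between V-1 and V-2 is 1/10 = 10% of an arm. The documents give neither the interval between these visits nor an expected dropout rate.

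**The case against.** The strongest reply is that the date of assignment is not the date of disclosure. No section says the operator is told the arm at V-1. The Manual of Procedures (Appendix C) is not in the reviewed text and might contain a release step. This stands: the documents support that the operator can know the arm, not that the operator does. A release step in Appendix C would answer most of the point, though 4.2 and Table 2 should still state it.

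Three stronger readings are tempting, and the documents do not support them.
- A reader might infer that decortication is optional and so open to selective use. Section 4.5 requires it in both groups; only the instrument is left open.
- A reader might infer that biased socket measurements would bias the bone results. As shown above, no specified bone analysis uses them.
- A reader might take 9.7% or 18.5% as the trial's false-positive rate. The shifts behind those figures are pure assumptions, and at 0.1 SD the rate barely moves. The same calculation would fit any bias of that size in a trial with 10 per arm.

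It is also fair to say that the benefit is limited. The operator must know the arm once saline or amnion is mixed. Packing, the decision whether to place an implant, the D1–D4 grade and torque all come later and are untouched by this change. The histology reading is already blinded. That blinding protects the reading, however, not the handling of the socket or the choice of site.

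**Conclusion.** The point holds at the strength given in the heading. Allocation precedes extraction on any reading of Table 2, the arm is needed only after extraction, and the reviewed text states nothing that withholds it in between. The operator can therefore know the arm during extraction, debridement and decortication and while socket defects are recorded, and the biopsy site may be chosen after allocation.

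Of these, socket handling and choice of biopsy site could bear on the bone outcomes; defect recording bears only on baseline comparability. The size of any bias cannot be derived from the documents. The range of 5.5% to 18.5% for shifts of 0.1 to 0.5 SD shows only how a trial of this size would respond. The unadjusted two-group tests in section 13.4 would not correct such a shift.

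The conclusion assumes that Appendix C holds no release procedure. The change is worth making because this bias route is avoidable at low cost, not because bias has been shown.

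**What to change.** Amend sections 4.2 and 4.6 and Table 2 as follows.

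1. Keep biopsy site selection at V-1 and require it to be recorded before allocation.
2. Move the randomisation mark to V-2. State who holds the smoking-stratified sequence and that it is sealed.
3. Release the assignment only after extraction, debridement, decortication and the 4.7.1–4.7.2 measurements are complete and recorded, immediately before the graft is mixed. The 4.7.3 measurements follow suturing and are not affected.

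The cost is protocol wording, sealed envelopes and a wait in surgery. The amnion is cryopreserved and freezer-stored (section 16.0), and the reviewed text gives no preparation time, so the length of the wait is unknown. If it is a problem, existing staff who are not operating can open the assignment and prepare the material out of the operator's view. The operator then still learns the arm only at grafting, although allocation itself would fall slightly earlier.

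The operator will know the arm from grafting onward in either case. The gain is confined to the pre-graft steps and to fewer losses between allocation and treatment.
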